years before exfoliation. Premature loss of primary molars can seriously affect the development of permanent dentition, including space loss and malocclusion. Moreover, second primary molars were reported to be the most susceptible to caries development at the 4 and 5-year-olds in studies conducted in different countries around the globe (Elfrink et al., 2006; Autio-Gold & Tomar, 2005; Holt, 1995, Holland & Crowley, 1982), with a predilection for their occlusal surfaces (Douglass et al., 1995; Bimstein et al., 1981). Pits and fissures on the occlusal surface of permanent molars are considered to favor biofilm formation and retention, which the rate of occlusal caries development and progression are comparatively higher than that of smooth surface caries (Batchelor et al., 2004; Brown, 1995). In primary second molars, the generally deeper pits and fissures, as well as the presence of buccal pits and palatal fissures at mandibular and maxillary second primary molars respectively, may also contribute to its caries prevalence (Bimstein 1981).

Incipient carious lesions occur when minerals from the enamel subsurface are being lost initially, which may progress to cavitated carious lesions requiring restorations if left untreated. Calcium and phosphate ions can be redeposited to demineralized enamel via the process of remineralization as crystal voids, enhancing the strength by creating a net mineral gain (Cochrane et al., 2010). Remineralization with appropriate agents has proven effective to treat incipient carious lesions (Mohd Said et al., 2017; Cochrane et al., 2010). The use of fluoride promotes the remineralization in incipient carious lesion. Fluoride facilitates adsorption of calcium ions to demineralized enamel surface, as well as substituting hydroxyl ions (OH⁻) to form fluorapatite, that have a strong acid resistance against demineralization (Featherstone, 1999).

Topical fluoride varnish (TFV) with 5% sodium fluoride in its content has proven effective in preventing caries among children and

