All tooth surfaces will be first wiped clean and dry by clean gauze and cotton swab for visual inspection of caries. A basic dental charting will be first performed, which the overall primary dentition will be further assessed and recorded based on the presence of decayed (d) missing (m), and filled (f) teeth, as recommended by the WHO in 2013.

Then the ball end of the CPI probes will be used to slide through the pits and fissures of primary molars to detect any enamel cavities or discontinuities. The status of the occlusal surfaces of primary molars will be recorded based on the ICDAS coding system (International Caries Detection and Assessment System Corrdinating Committee, 2009; Ismail et al., 2007).

Children who do not meet all the inclusion criteria will be given an examination report. Parents will be informed regarding the carious teeth and will be advised to seek treatment from private dental practitioners or specialist paediatric dentists promptly. Children with second primary molar(s) that fulfill all the criteria will be included in the study.

The occlusal fissures of each of the upper and lower molars included in the study will be assessed, and the fissure morphology (deep/shallow) and ICDAS score will be recorded.

Randomization and treatment allocation

By using the random numbers generated by stratified block randomization method in a personal computer, children will be randomly allocated to one of the two study groups:

(1) NaF varnish

— Application of a 5% NaF varnish (Duraphat, Colgate-Palmolive Ltd, Waltrop, Germany) on the occlusal surfaces of primary second molars and all other teeth, every 3 months during the study period;

(2) GI sealant

-- Glass ionomer sealant (GC Fuji VII® (pink)) on all primary second molars included in the studies, with no further repair/replacement of the sealant

Interventions

Immediately after the oral examination, a chair-side dental assistant will prepare the materials respective to the groups allocated on the random allocation list.

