A 10% random sample will be re-examined during every examination to monitor intra-examiner reproducibility.

An oral health talk will be given to the parents of the participants. During the talk, the parents will be instructed to choose fluoridated toothpastes and child toothbrushes throughout the period of study. In case of any adverse event during the study, the parents will be advised to contact the principal investigator.

Outcome measures

The primary outcome measure is carious cavity development into dentin (ICDAS code 4, 5 and 6) on the occlusal surfaces of primary second molars over time.

Only one registered dentist will be the examiner in the kindergarten throughout the whole 24-month study period. She will receive training and calibration by epidemiologists before examining the subjects. The following dental equipment will be used:

- (1) Disposable dental mirror attached to a handle with light-emitting diode intra-oral illumination
- (2) World Health Organization CPI periodontal probe(405/WHO probe)

A 10% random sample will be re-examined during every examination to monitor intra-examiner reproducibility. The ICDAS score will be recorded based on the index proposed by Ismail et al., 2007.

Parents will be notified about the development of carious lesions. Advice on oral hygiene maintenance and seeking private dentists for respective dental treatments will be given to the parents in the form of a detailed report.

The proposed study will be a randomized controlled trial with 2 parallel groups. The unit of randomization will be each individual participant, but not each tooth of the mouth.

(iv) Data processing and analysis

Data analysis will be performed using SPSS® Statistics version 23.0 (SPSS Inc, Chicago, IL, USA). All children with missing data resulting from loss to follow-up or unrecorded data will be excluded from the analysis. Data proof-reading will be performed after data entry to identify and correct any errors before analyzing the data. An intention-to-treat analysis will be undertaken. Intra-examiner agreement in the diagnosis of dental caries will be assessed by Cohen's Kappa statistics.

Chi-square test will be used to assess the difference between groups according to the distribution of children's demographic characteristics such as gender, place of birth, oral health-related behavior, use of fluoride toothpaste, snacking habit, parents' education and family income.

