The outcome measures are the mean change in the overall dmft scores and ICDAS code in primary second molars over time. Within-group comparison of changes in mean overall dmft scores and ICDAS scores at 24 months and mean change in overall dmft scores and ICDAS scores will be assessed by applying repeated analysis of variance (ANOVA) (or Friedman test for non-parametric data).

Student's t-test will be applied to differentiate the comparability between the treatment groups according to the subject's baseline conditions, including the child's age, dmft score and VPI score.

Since more than one molar will be included from one child, GLIMMIX procedure will be used to adjust for the clustering effect. The first level and second level will be the primary second molar and the subject

respectively. This analysis accounts for the correlation (clustering) between observations of multiple molars from the same child.

A multi-level logistic regression analysis will be performed to analyze the effects of independent variables on the ICDAS scores at the 6, 12, 18 and 24 month examinations. The independent variables included the child's demographic characteristics, oral health-related behaviors and clinical characteristics (gender, place of birth, frequency of tooth brushing, use of fluoride toothpaste, snacking habits, mother's education, father's education, family income, VPI score, dmft score and the treatment group). The level of statistical significance for all tests will be set 5%.

Key References:

3. American Academy of Pediatric Dentistry. Guideline on caries-risk assessment and management for infants, children, and adolescents. *Pediatr Dent.* 2013;35(5): E157-64.
4. American Dental Association Council on Scientific Affairs. Professionally applied topical fluoride: evidence-based clinical recommendations. *J Am Dent Assoc.* 2006;137(8): 1151-9.

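### Fissure morphology is graded on every study molar at baseline but has no stated use in the analysis; adding it as a molar-level covariate would be a small, free gain

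*Combined protocol and SAP*

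**What the plan says.** The Introduction, section b), gives the rationale. It names "In primary second molars, the generally deeper pits and fissures, as well as the presence of buccal pits and palatal fissures" among features that might add to caries in these teeth. The wording is tentative and describes second primary molars as a tooth type.

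Section d)(iii), Tooth status, says that for each included upper and lower molar "the fissure morphology (deep/shallow) and ICDAS score will be recorded". This happens before treatment is given.

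Randomisation in d)(iii) is described only as follows: "By using the random numbers generated by stratified block randomization method in a personal computer". No strata are named. Allocation is by child: "The unit of randomization will be each individual participant, but not each tooth of the mouth".

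Section d)(iv) sets up a two-level model with the molar at the first level and the child at the second. The bracketed list of independent variables for the multi-level logistic regression runs from gender and place of birth through brushing, toothpaste, snacking and parental education to "family income, VPI score, dmft score and the treatment group". All of these belong to the child. The baseline comparisons name demographic and behavioural items (chi-square test) and age, dmft and VPI (t-test). Fissure morphology appears in none of these lists, and no subgroup or sensitivity analysis mentions it.

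**The concern.** The plan builds a molar level into its model and then puts no molar characteristic in it. Fissure form is the obvious candidate. The protocol links it tentatively to the disease, and sealants are described as working by closing pits and fissures. It is also measured before treatment, at no extra cost.

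The listed covariates do not clearly stand in for it. VPI is scored on buccal and palatal or lingual surfaces, not occlusal ones. The spread of baseline dmft is narrowed by the eligibility rules.

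Two things are at stake, both modest. If the arms differ by chance in their share of deep fissures, the planned model cannot take that into account. And because the variable will be in the data set with no stated role, a decision to adjust for it could be taken after results are known.

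**Working it through.** The plan states no figure on this point, so there is none to reproduce. Its evaluable sample size is taken as given.

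**Inputs**

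- n = 102 children per arm: d)(ii), Sample size calculation.
- m = 4 molars per child: assumed (all four second primary molars included).
- Share of molars graded deep, p: 30-70%, assumed.
- Within-child ICC of depth: 0.3-1, assumed.
- Odds ratio for dentin caries, deep versus shallow: 2-4 in step 2 and 1.5-3 in steps 3 and 4, assumed.
- Mean risk of dentin caries: 20%, assumed (step 3 only).

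**Step 1: size of the chance imbalance.** The SD of the between-arm difference in the share deep is sqrt[ 2p(1-p)/n × (1+(m-1)ICC)/m ].

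- p = 0.5, ICC = 1: sqrt(2 × 0.25/102) = 0.070.
- p = 0.5, ICC = 0.6: sqrt(2 × 0.25/102 × 2.8/4) = 0.059.
- p = 0.3 or 0.7, ICC = 0.3: sqrt(2 × 0.21/102 × 1.9/4) = 0.044.

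The SD is therefore 4.4 to 7.0 points, with a 95% range of about ±9 to ±14 points. The chance of an imbalance above 10 points is 2% to 15%.

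**Step 2: effect on the treatment odds ratio.** By log-linear approximation the factor is exp(k × SD × ln OR) for a k-SD imbalance. With p = 0.5:

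| Imbalance | ICC | Fissure OR 2 | Fissure OR 4 |
|---|---|---|---|
| 1 SD | 0.6 | 1.04 | 1.08 |
| 1 SD | 1 | 1.05 | 1.10 |
| 2 SD | 0.6 | 1.08 | 1.18 |
| 2 SD | 1 | 1.10 | 1.21 |

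**Step 3: effect on the risk difference.** With 20% mean risk and half the molars deep, a fissure OR of 2 means risks of 14.6% (shallow) and 25.4% (deep). A 10-point imbalance then shifts the risk difference by 0.10 × (25.4 - 14.6), about 1.1 points. For fissure ORs of 1.5 and 3 the shift is 0.6 and 1.7 points.

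**Step 4: does the planned test stand without the covariate?** Logistic regression with cluster-robust errors was simulated in 1,500 replicates, with 102 children per arm, four molars each and fissure OR 1.5-3. Power is at an assumed treatment odds ratio of 0.45.

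| | Without depth | With depth |
|---|---|---|
| Type I error | 5.1-5.6% | 5.2-5.6% |
| Power | 88.9-90.3% | 88.9-90.9% |

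The error rate holds, and power hardly changes.

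**Step 5: scale.** About 90% power at an odds ratio of 0.45 implies SE(log OR) ≈ |ln 0.45|/(1.96 + 1.28) = 0.80/3.24 ≈ 0.25. The 95% interval then extends by a factor of about exp(1.96 × 0.25) ≈ 1.6 each way. Even the 1.21 from step 2 lies well inside it.

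**The case against.** The best case for leaving the plan alone has several parts.

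- **Chance imbalance is already covered.** In a randomised trial the unadjusted test and interval allow for it, and step 4 bears this out. This stands. A reader might infer that the omission biases the comparison or invalidates the test; the documents do not support that.
- **The protocol does not show that depth is prognostic among study teeth.** Its remark concerns second primary molars as a type, and every study tooth is one. The related sentence on biofilm is about permanent molars: "Pits and fissures on the occlusal surface of permanent molars are considered to favor biofilm formation and retention". This stands. To call depth an established cause of the outcome goes beyond the text, and the odds ratios above have no source in it.
- **The larger figures are unfavourable cases.** They combine a 2-SD imbalance, maximum variance at 50% deep and, at ICC 1, depth fully shared within a child. In that last case a child's molars do not differ in depth, so no between-molar variation is lost, and the child-level term already models that variance. This stands, although a child-level term does not correct a difference between arms.
- **Adjustment is not a pure precision gain.** In a logistic model it changes which conditional odds ratio is estimated. Deep and shallow have no stated criteria, and the kappa check covers only caries diagnosis, so grading error would weaken the adjustment. Both limit the benefit.
- **The absence is not total proof of non-use.** The baseline lists are worded as examples, and the randomisation strata are unnamed. But depth varies by tooth while allocation is by child, and no text says depth was a stratum. The regression list is enumerated in full.

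Jaw might seem to need the same treatment. It does not: a child with upper and lower molars included contributes both to the same arm, so jaw is largely balanced by design.

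**Conclusion.** The gap is real and minor. A molar-level baseline variable, recorded before treatment and tentatively linked by the protocol to the disease, is missing from an enumerated covariate list that is entirely child-level, and no other use is stated. The cost is a missed chance to guard against chance imbalance and to settle the variable's role in advance. It is not a flaw in validity, and no meaningful gain in power should be expected.

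The quantities in the working depend on assumed values for deep-fissure prevalence, within-child correlation and fissure effect. If deep and shallow second molars carry much the same risk, adjustment would change almost nothing.

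The same sentence of the protocol records the baseline ICDAS code, which is also absent from the covariate list. Under d)(i), second molars with codes 4, 5 or 6 are excluded, so study molars can enter at codes 0 to 3 on the scale that defines the outcome. That covariate has at least as strong a claim to inclusion.

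**What to change.** In d)(iv), add one sentence that prespecifies baseline fissure morphology (deep/shallow) and baseline ICDAS code as first-level (molar) covariates in the multi-level logistic regression. Show fissure morphology by arm in the baseline table. A line on how deep and shallow are told apart would make the grading reproducible.

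Jaw need not be added, and a separate report of the treatment effect in deep and shallow fissures is not required. The trial is not sized for it. If the effect by depth is reported, label it exploratory and base it on an interaction test.

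The cost is a few lines of text and one table row. No new data, visits or participants are needed.

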fissure sealants are significantly more effective than topical fluoride varnishes in preventing occlusal caries in permanent molars (Levy, 2012; Liu et al., 2012). However, a recent Cochrane review suggested that there was still insufficient evidence to determine superiority of resin or glass ionomer fissure sealants over topical fluoride varnishes for occlusal caries prevention, due to the lack of reliable results and low quality of evidence (Ahovuo-Saloranta et al., 2016).

Also, most studies were conducted on permanent first molars among school children (Ahovuo-Saloranta et al., 2016), whom cooperation and moisture control can be easily achieved. However, application of fissure sealants, especially resin-based sealant, in very young children can be a technique-sensitive procedure. Compared with a mean treatment time of less than 3 minutes for varnish application, application of resin-based sealants required over 15 minutes (Splieth et al., 2001). Moisture control is also of paramount importance for the retention and success of resin-based sealants (Gooch et al., 2009), which may be difficult among young preschool children.

Glass-ionomer sealants can chemically bond to enamel and are more tolerable to inadequate moisture control (Antonson et al., 2012). As its application requires less clinical steps, glass-ionomer sealant is comparatively more acceptable to younger patients and can be used in outreach settings with a large number of participants. The fluoride releasing ability is also beneficial in preventing caries especially at adjacent tooth surfaces (Cagetti et al., 2014). However, its retention rate is significantly lower than that of resin-based sealants (Antonson et al., 2012), its success rate in preventing fissure caries in very young patients is still unknown.

c) Aims and Hypotheses to be Tested:

Aims

To compare the efficacy of glass ionomer fissure sealant versus topical application of 5% sodium fluoride varnish in prevention of occlusal caries among preschool children.

Hypotheses to be tested

Greater reduction in occlusal caries in preschool children by glass ionomer fissure sealant compared to topical application of 5% sodium fluoride varnish.

d) Plan of Investigation:

(i) Subjects

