4	Underlying dark shadow from dentin with or without localized enamel breakdown	The carious lesion appeared like a shadow of discolored dentin appeared through an apparently intact enamel, which might show signs of localized breakdown.
5	Distinct cavity with visible dentin	Cavitation in opaque or discolored enamel exposing the dentin beneath, involving less than half of the tooth

		surface.
6	Extensive distinct cavity with visible dentin	Cavitation in opaque or discolored enamel exposing the dentin beneath, involving at least half of the tooth surface. Obvious loss of tooth structure and dentin is clearly visible on the walls and at the base in a cavity that involved at least half of the tooth surface.

Questionnaire survey

Parents are required to complete a validated questionnaire before the baseline examination, which consists of the following sections:

- (1) The child's personal information - gender, age, place of birth, medical history of systemic disease and long term medication
- (2) The child's oral health-related behaviors – snacking habit, frequency of toothbrushing, parent's supervision in toothbrushing, use of toothpaste and night bottle habit
- (3) The child's dental history – past dental treatment received
- (4) The child's socio-economic background - parents' age, education level, household income and number of children

(iii) Study design

Clinical exam

Clinical examination will be carried with the child lying supine on table provided by the kindergarten.

The Visible Plaque Index (VPI) (Ainamo & Bay, 1975) will be used to measure the oral hygiene status of the child. Buccal and palatal/lingual surfaces of 6 index teeth (teeth 55, 51, 63, 71, 75, 83) will be examined. The presence or absence of visible plaque on the tooth surfaces mentioned above will be recorded as "1" or "0" respectively. The VPI score of the child will be obtained by dividing the number of

tooth surfaces recorded as “1” with the total number of tooth surfaces recorded as “0” and “1”, i.e.

$$\text{VPI} = \frac{\text{number of tooth surfaces recorded as “1”}}{\text{total number of tooth surfaces recorded as “0” and “1”}}$$

b. Tooth status

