For the sealant group, glass ionomer sealants will be applied using the finger pressure technique described in the WHO manual for atraumatic restorative treatment (ART) (Frencken et al.; 1997). The primary second molars included in the study will first be cleaned and dried by wiping with gauze and cotton pellets. Following the manufacturer's instructions, further cleaning of the fissures will be performed by applying GC cavity conditioner with micro-applicator for 10-15 seconds, then clean with wet cotton pellets for several times. The surface will be dried with cotton pellets. The dental assistant will mix the glass ionomer sealants (GC Fuji VII) in a standardized proportion with an amalgamator. Glass ionomer sealants will be applied to the occlusal surface with blunt end of an applier and slightly overfilled. A gloved finger with petroleum jelly will be used to push and rub the materials into the pits and fissures, as well as removing the excess sealants from the tooth surfaces. The sealants will be covered and protected by a layer of petroleum jelly (Vaseline®).

In the NaF varnish groups, 0.25mL (one drop) of the varnish will be placed in a plastic dappen dish. A disposable microbrush will be used to apply the varnish onto the second primary molars included in the study and all other teeth. The child will be instructed not to eat or drink after the application of varnish for at least half an hour.

Follow-up evaluation

Children in the NaF varnish group will be recalled at the 3rd, 6th, 9th, 12th, 15th, 18th, 21st and 24th months for reapplication of fluoride varnish. Similar to baseline, 0.25mL (one drop) of the 5% sodium fluoride varnish will be applied using a disposable microbrush. At the 6th, 12th, 18th and 24th months, a clinical examination will be performed for all children in both groups. During the follow-up examination, overall VPI and dmft will be recorded. ICDAS score will be recorded for each primary second molar included in the study.

Sites with sealant will be evaluated in the following aspects:

Aspect	Code	Classification	Description
Retention	0	Fully intact	Sealants are fully intact without apparent loss of materials.
	1	Partial loss	Sealants are retained with partial loss
	2	Total loss	No sealant materials are found on tooth surface.
Caries	0	No caries	No caries found at the margin of the sealants.
	1	Presence of caries	Evidence of caries found at the margin of the restoration.

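### One dentist scores every primary-outcome examination with no masking described, and the sealant-only retention codes require the scorer to know the arm even when no sealant remains

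*Combined protocol and SAP*

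**What the plan says.** Under Outcome measures, the opening statement reads: "The primary outcome measure is carious cavity development into dentin (ICDAS code 4, 5 and 6) on the occlusal surfaces of primary second molars". The same section says that "Only one registered dentist will be the examiner in the kindergarten throughout the whole 24-month study period", and of this dentist that "She will receive training and calibration by epidemiologists before examining the subjects". A 10% random sample is re-examined at each examination, and intra-examiner agreement is summarised by Cohen's kappa.

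Under Follow-up evaluation, both arms are examined at months 6, 12, 18 and 24, with ICDAS recorded for each study molar. A table of retention and margin-caries codes follows, introduced by "Sites with sealant will be evaluated in the following aspects". Retention code 2 is total loss, defined as no material on the tooth. The varnish arm also returns every 3 months for re-application, which includes all four examination months.

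Under Randomization and treatment allocation, the second arm is "Glass ionomer sealant (GC Fuji VII® (pink)) on all primary second molars included in the studies", with no resealing during the study. Under Interventions, directly after the baseline examination, "a chair-side dental assistant will prepare the materials respective to the groups allocated on the random allocation list".

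The text describes no masking of the examiner, no separation of examiner and operator, no withholding of the allocation list at follow-up, and no second reader.

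**The concern.** The event is a clinical call at a threshold. For ICDAS 4, the lowest code that counts, the table says: "The carious lesion appeared like a shadow of discolored dentin appeared through an apparently intact enamel". The step from code 3 to code 4 decides whether a molar is an event, and one person takes that step for every child.

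If that person knows the arm, any difference in threshold between arms passes straight into the treatment contrast. The clustering and covariate adjustments in the analysis section cannot remove it, and no second reading could reveal it. The hypothesis is directional, in favour of sealant.

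The avoidable part is what matters. Visible pink material discloses the arm whatever the plan says. The total-loss code discloses it where the tooth no longer would. The Introduction accepts of glass ionomer that "its retention rate is significantly lower than that of resin-based sealants", and with no resealing some loss has to be expected over 24 months.

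**Working it through.** **1. What the codes require.** Three statements are set side by side.

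- ICDAS is scored for every study molar in both arms.
- Retention and margin items are scored for sealed sites only.
- Retention code 2 applies when nothing is left on the tooth.

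A bare molar in the varnish arm gets no retention code. A bare molar in the sealant arm gets code 2. The two teeth may look alike, so the scorer needs the allocation, or a record that reveals it, to know which entry to make. No assumption about workflow is needed for this step.

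**2. What the visit routine establishes.** At baseline the materials are prepared after the examination, so that step does not disclose the arm before baseline scoring. At months 6 to 24, varnish and examination fall in the same months with no stated order. The documents do not say who applies treatment or who attends the varnish-only visits at months 3, 9, 15 and 21. Disclosure by this route is possible but not established.

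**3. What the quality checks can detect.** Calibration precedes the examinations. Kappa compares the examiner with herself. A threshold that differs consistently by arm would repeat on re-examination and is compatible with high kappa.

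**4. Illustration of size (assumed error rates, no true effect).** The plan gives no figure for measurement error, so there is none to reproduce. With true risk p, sensitivity Se and specificity Sp:

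observed rate = p × Se + (1 − p) × (1 − Sp)

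Take Se = 0.90 in both arms, Sp = 0.98 (sealant) and 0.94 (varnish).

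| p | Sealant | Varnish | Ratio |
|---|---|---|---|
| 0.10 | 0.090 + 0.018 = 0.108 | 0.090 + 0.054 = 0.144 | 0.75 |
| 0.20 | 0.180 + 0.016 = 0.196 | 0.180 + 0.048 = 0.228 | 0.86 |
| 0.30 | 0.270 + 0.014 = 0.284 | 0.270 + 0.042 = 0.312 | 0.91 |

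Swapping the two specificities reverses the result. At p = 0.10 the ratio becomes 0.144 / 0.108 = 1.33. The direction is therefore an input, not a finding.

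**5. Effect on the test.** Use the protocol's 102 evaluable children per arm, a two-sided 5% test and a normal approximation with one binary outcome per child. For observed rates a and b, let d = |a − b|, SE0 = √(2p̄(1 − p̄)/n) with p̄ the mean of a and b, and SE1 = √((a(1 − a) + b(1 − b))/n). The rejection probability is Φ((d − 1.96 SE0)/SE1) + Φ((−d − 1.96 SE0)/SE1). With equal true risk between 10% and 40%:

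| Assumed Se, varnish / sealant | Assumed Sp, varnish / sealant | Observed ratio | Rejection |
|---|---|---|---|
| 0.90 / 0.80 | 0.95 / 0.95 | 0.93 to 0.90 | 5.5% to 9.1% |
| 0.90 / 0.70 | 0.95 / 0.95 | 0.85 to 0.79 | 7.2% to 22.3% |
| 0.95 / 0.85 | 0.90 / 0.95 | 0.70 to 0.84 | 17% to 19% |

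**6. How much masking could remove.** Randomisation is by child and every study molar of a sealant child is sealed, so one pink remnant identifies the whole mouth. Let r be the share of sealant children with visible material on at least one study molar. If children without visible material are all scored at one threshold, and true risk does not depend on retention, the remaining gap is r × the original gap. At r = 1 nothing is removed; at r = 0 all of it is. The documents give no value for r, so the figures in steps 4 and 5 overstate what the fix can recover.

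**The case against.** The plan is silent on masking; it does not declare the examiner unmasked. No case report form is shown, only a code table, and the text mentions ICDAS before the sealant items. A reader might infer that the visit routine shows the examiner the arm. The documents do not support that, because preparation of materials falls to an assistant after the baseline examination, and operator and visit order are unstated. This objection stands for the workflow. It does not answer the total-loss code, because nobody other than the one dentist is named as scoring.

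A reader might also infer a bias of 9% to 25% in favour of sealant. That is not supported. The error rates have no source, and the extra margin-caries inspection of sealed sites could push the other way. Nor can these percentages be set against the 30% in the sample size section, which does not say whether it is absolute or relative.

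The outcome is not wholly subjective. A ball-ended probe is used, and codes 5 and 6 require visible dentin. Training and calibration are planned, so kappa is not the only safeguard. These points lower the likely error but do not address a lean by arm.

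It is tempting to say that every molar without sealant could be masked at almost no cost. Step 6 shows otherwise: any remnant elsewhere in the mouth gives the arm away. The lower retention quoted from the Introduction rests on a study whose title concerns partially erupted permanent first molars, so it gives no rate of total loss for primary molars.

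**Conclusion.** The concern holds in a limited form. One dentist makes every primary-outcome call, no masking is described, and the follow-up codes as written require knowledge of the arm even when the mouth does not show it. The planned reliability checks would not reveal a consistent difference in threshold. Disclosure through the visit routine is a possibility that the plan leaves open.

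The size and direction of any bias cannot be derived from the documents. The illustrations show only that modest differences in error rates can imitate a benefit or a harm. They rest on assumed sensitivities and specificities and on child-level binary outcomes, and they include bias that masking cannot remove.

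This should be changed because the remedy is cheap. It is not a fatal flaw, and no sample-size figure depends on it.

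**What to change.** At months 6, 12, 18 and 24:

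1. The examiner scores ICDAS for every study molar in both arms first, without the allocation list or earlier records. The sheet identifies the child and the study molars only, and children of both arms are seen in mixed order.
2. One common form then records visible sealant (full, partial or none) for every study molar in both arms. The margin item follows, and only where material is visible. Total loss and all sealed-site summaries are derived later by linking to the allocation list.
3. Varnish is re-applied only after scoring is finished. The interval and amount are not touched.
4. Where existing staff allow, the examiner neither applies treatment nor attends the varnish-only visits. The protocol should state who does.
5. The protocol states that masking is partial. It is not possible in a child with any visible sealant, or if the examiner is also the operator.

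Reporting kappa by arm is not a remedy. It cannot detect a consistent lean, and 10% of 256 is about 26 children, or 13 per arm.

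The cost is a revised form, a changed visit order and protocol wording. Item 4 may need another operator if the dentist currently treats. Masking remains incomplete throughout.
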